9.3 Primary Analysis

The primary outcomes of incidence of maternal death or sepsis and incidence of intrapartum/neonatal death or sepsis will be compared between the two treatment arms using generalized linear models. These generalized linear models will be fit with each binary outcome separately as the outcome measure. Estimates of relative risk and associated 95% confidence intervals will be reported. The model will include terms for treatment and site. As randomization occurs at the pregnancy level and approximately 1-2% of pregnancies are anticipated to be multiple gestations, models for neonatal outcomes will account for correlation among multiples assuming an exchangeable covariance structure. If a model for neonatal outcomes has convergence issues, then the generalized linear model will be fit without the adjustment for correlation among multiples. For the two primary outcomes, these analyses will be conducted using the ITT population and the p-values associated with the treatment term will be used to formally test each of the two primary hypotheses at the alpha = 0.05 level.

The primary analyses using the ITT population will use multiple imputation for missing outcomes implemented separately for mothers vs. infants via logistic regression imputation using site and high-risk status prior to randomization as covariates. As sensitivity analyses, the primary outcomes will also be analyzed without imputation for individuals in the ITT population, without imputation for individuals in the per-protocol population; and in the ITT population assuming all missing outcomes are sepsis or death as well as assuming all missing outcomes are not sepsis nor death.

As secondary analyses of the primary outcomes, the models will be run including region (Africa, Latin America, or Asia) and a treatment by region interaction term. If the interaction term has a $p<0.1$, then effect estimates and associated confidence intervals will be reported by region with treatment effect within region for Africa and Asia tested at the 0.025 level.

For secondary publications, additional exploratory models will also be run including individually: 1) a treatment by site interaction term, 2) any other antibiotic use during labor (yes or no) and its interaction with treatment, and 3) mode of delivery (cesarean or vaginal) and its interaction with treatment. If the interaction term for any of these models has a $p<0.1$, then effects will also be reported by the relevant subgroups. These exploratory secondary models will also include any demographic or clinical variables found to differ significantly between the treatment arms in the preliminary analyses described above. From each final model, adjusted relative risk estimates for treatment will be obtained. Kaplan-Meier survival curves will be fit to the data in order to get cumulative incidence curves by treatment group of the timing of the first occurrence of maternal death or sepsis and intrapartum/neonatal death or sepsis.

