3.1 Statistical Analysis Plan

3.1.1 Primary Analyses

Incidence of maternal death or sepsis and intrapartum/neonatal death or sepsis will be compared between the two treatment arms using generalized linear models. These generalized linear models will be fit with each binary outcome separately as the outcome measure. Estimates of relative risk and associated 95% confidence intervals will be reported. The model will include terms for treatment and site. As randomization occurs at the pregnancy level and approximately 1-2% of pregnancies are anticipated to be multiple gestations, models for neonatal outcomes will account for correlation among multiples assuming an exchangeable covariance structure. For the two primary outcomes, these analyses will be conducted using the ITT population and the p-values associated with the treatment term will be used to formally test each of the two primary hypotheses at the alpha = 0.05 level.

As secondary analyses of the primary outcomes, assuming an overall treatment effect is observed, the models will be run including region (Africa, Latin America, or Asia) and a treatment by region interaction

term. If the interaction term has a $p < 0.1$, then effects will be reported by region with treatment effect within region tested at the 0.025 level.

Additional exploratory models will also be run including individually: 1) a treatment by site interaction term, 2) any other antibiotic use during labor (yes or no) and its interaction with treatment, and 3) mode of delivery (cesarean or vaginal) and its interaction with treatment. If the interaction term for any of these models has a $p < 0.1$, then effects will also be reported by the relevant subgroups. These exploratory secondary models will also include any demographic or clinical variables found to differ significantly between the treatment arms in the preliminary analyses described above.

From each final model, estimates of relative risk associated with treatment will be obtained including unadjusted estimates of risk from the primary model as well as estimates of risk adjusted for potential confounders from the secondary analyses.

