6. SAMPLE SIZE DETERMINATION

6.1 Overall (All-comer) Sample Size for Primary Outcomes

Sample size estimates were generated to evaluate the potential benefits of peripartum prophylactic azithromycin to reduce the risk of adverse maternal and neonatal outcomes in two population cohorts of women in low and low-middle income settings. The first population of interest comprises all women delivering in facilities (overall).

Power calculations for the study in the overall study population were generated for two primary outcome measures, one being the risk of maternal death or sepsis among women in the target population and the other being intrapartum /neonatal death or sepsis in infants delivered by women in the target population. For each of these outcome measures estimates of the required sample size needed to detect a risk reduction of 20%, 25%, and 30% were generated for power of 0.8, 0.85, and 0.9. The risk of sepsis or maternal death was assumed to be 3%. That number is slightly higher than the current risk in the GN population, which is slightly less than 2%. However, we anticipate that with active surveillance rather than passive reporting based on the new WHO

definition of maternal sepsis (designed to catch more cases of sepsis), the risk will be at least 3%. For the neonatal outcome, the underlying risk of the combined outcome of intrapartum stillbirth, neonatal death, or sepsis was assumed to be between approximately 8% and 14%. This estimate was based on recent data from the GN indicating that the risk of intrapartum stillbirth is approximately 1.8% and the risk of neonatal death during the first 28 days after delivery is 2.3%; we assumed that the risk of sepsis not resulting in death is approximately 4% to 10%. The resulting required evaluable sample sizes are shown in Table 1 below.

Table 1. Sample Sizes for the Overall Population, Alpha=0.05

Baseline Risk	Risk Reduction	Evaluable Sample Size per Arm		
		Power=0.80	Power=0.85	Power=0.90
3%	20%	11455	13103	15334
3%	25%	7133	8159	9548
3%	30%	4815	5508	6446
8%	20%	4096	4686	5483
8%	25%	2554	2921	3419
8%	30%	1727	1975	2311
14%	20%	2204	2521	2950
14%	25%	1377	1575	1842
14%	30%	932	1066	1247

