7.5 Multiple Comparisons and Multiplicity

There is one formal hypothesis test for each of the maternal and neonatal population of the study. Each population will be analyzed and interpreted separately and thus analyses are not adjusted for multiplicity between these populations. The statistical test of the primary outcome in each population will be conducted at an overall 5% type I error rate (two-sided) with p-value allocation between the interim and final analyses as detailed in Section 11.

The study sample size was determined to provide sufficient power to test for treatment effects within the high-risk cohort as the main secondary aim and also within region. As these are secondary aims, no adjustment multiplicity was applied to the planned primary study analyses. However, to avoid over-interpretation of regional findings the sub-analysis of the primary neonatal outcome within the Asian and African regions will be conducted controlling the Type I error rate at the 0.025 level.

However, all other analyses of secondary outcomes are exploratory in nature; therefore, p-values and confidence intervals are provided for descriptive purposes only. Additionally all p-values provided for any baseline and demographic characteristics and safety parameters will be for descriptive purposes only. As such, unless otherwise specified, p-values presented will be on a per analysis basis, with no further control for multiple tests.

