The details of the timing of the interim analysis as well as the approaches for correcting for multiplicity and analyzing conditional power were determined in collaboration with the DMC. The single, formal interim analysis of efficacy and futility will be conducted after approximately 70% of women have been enrolled and reached primary endpoint. Interim analyses will be conducted using the overall study population and the primary analytic approach detailed in Section 9.3. Cut-off p-values for testing for efficacy at this interim analysis will be determined based on a Bonferroni-type correction for multiple comparisons with a nominal α of 0.0001 at the interim analysis and a nominal α of 0.0499 for the final analysis (Casella and Berger 2002). Specifically, if the p-values are < 0.0001 for the treatment versus placebo comparison, then the DSMC may recommend stopping enrollment. The DMC can recommend stopping enrollment for futility if the conditional power is less than 0.5 at this time.

Additionally, the DMC will review the study at periodic intervals, to evaluate whether any safety or study progress issues warrant possible study stopping. These periodic reviews are based on DMC reports prepared by the Data coordinating center, which included information on study enrollment rates and participant progress through the study, protocol violations, adverse events, and efficacy outcomes. The focus of the DMC review is on monitoring participant safety and study progress/futility but data on treatment effectiveness will also be presented to frame the DMC discussions on safety and futility.

The DMC will also review the study for study progress and futility, with futility for these analyses defined in terms of inability to achieve study enrollment goals. To effectively complete the study within the parameters defined by NICHD and the Global Network Steering Committee, the goal of study is to complete enrollment in a 24-month period, and enrollment be completed within 30 months. Should the DMC have concern about study progress, the DMC will request from the protocol committee an action plan for increasing enrollment that should be delivered to the DMC for review within a 1-month period. Should the DMC consider the plan inadequate or should the plan not result in increased enrollment by the next review, the DMC may consider recommending to the NICHD closing the study for futility.

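### If a neonatal model fails to converge, SAP 9.3 drops the clustering of multiples and names no robust variance; the resulting error is small, and its direction depends on a distribution the SAP does not state.

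*Combined protocol and SAP*

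**What the plan says.** Protocol 3.1.1 and SAP 9.3 both plan generalized linear models with terms for treatment and site, reporting relative risks. Both state that "models for neonatal outcomes will account for correlation among multiples assuming an exchangeable covariance structure". SAP 9.3 gives the reason, "As randomization occurs at the pregnancy level", and the scale: "approximately 1-2% of pregnancies are anticipated to be multiple gestations".

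The SAP then adds a rule that the protocol does not have. If a neonatal model has convergence issues, "then the generalized linear model will be fit without the adjustment for correlation among multiples". No robust variance or intermediate step is offered. Neither document names the distribution or link. SAP Section 12, reserved for changes from the protocol's analyses, carries no entry.

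The models are used to "formally test each of the two primary hypotheses at the alpha = 0.05 level". SAP 11 splits this into a "nominal α of 0.0001 at the interim analysis and a nominal α of 0.0499 for the final analysis". SAP 9.3 runs the primary ITT analysis on multiply imputed outcomes, and SAP 9.5 analyses binary secondary outcomes in a similar way.

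**The concern.** Co-twins always receive the same treatment, and their outcomes are likely to be positively correlated. A fit that counts them as independent overstates the information in the data. If its variance is the binomial one, confidence intervals are too narrow and the test rejects too often.

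The rule covers any neonatal model, so it reaches a primary outcome, the high-risk cohort and interaction models of SAP 9.4, and the binary neonatal secondary outcomes. Some of those are rare, such as pyloric stenosis or neonatal death due to sepsis.

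The rule may also miss the cause. A relative-risk model can fail because of its link or because of sites with few events, and removing the correlation changes neither. If only some imputed data sets fail, nothing says whether all are refitted, so clustered and unclustered variances could be pooled.

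**Working it through.** **Inputs from the documents.** Multiple gestations 1-2% of pregnancies (SAP 9.3); neonatal risk 8-14%, 34,000 women, 2-3% loss, 37.5% of women in Africa and 50% in Asia, regional alpha 0.025 (SAP 6.1); final alpha 0.0499 (SAP 11); two-sided tests (SAP 7.5).

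**Assumptions not in the documents.** Within-pair correlation ρ, shown from 0.3 to 1.0; all multiples are twins; twins carry the same risk as singletons unless stated.

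**The plan's own figure.** Table 1 gives 5,483 per arm for 8% risk, a 20% reduction and 90% power. The pooled two-proportion formula gives [1.960·√(2·0.072·0.928) + 1.2816·√(0.08·0.92 + 0.064·0.936)]² / 0.016² = 5,482.8, which rounds up to 5,483. All 27 cells of Table 1 reproduce. This calculation treats infants as independent.

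**Binomial model-based variance.** With twin fraction f per pregnancy, the design effect is DE = 1 + ρ·2f/(1+f). The multiplier of ρ is 0.02/1.01 = 0.0198 at f = 1% and 0.04/1.02 = 0.0392 at f = 2%. The unclustered standard error is too small by 1 − 1/√DE, and the true error of a 5% test is 2·[1 − Φ(1.96/√DE)].

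| f | ρ | DE | SE too small by | True error of a 5% test |
|---|---|---|---|---|
| 1% | 0.3 | 1.006 | 0.3% | 5.07% |
| 1% | 0.5 | 1.010 | 0.5% | 5.11% |
| 1% | 1.0 | 1.020 | 1.0% | 5.23% |
| 2% | 0.3 | 1.012 | 0.6% | 5.14% |
| 2% | 0.5 | 1.020 | 1.0% | 5.23% |
| 2% | 1.0 | 1.039 | 1.9% | 5.45% |

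In the last row, the final alpha of 0.0499 becomes 0.0544 and the regional 0.025 becomes 0.0279. A conclusion changes only if the unclustered z lies between 1.96 and 1.96·√1.0392 = 1.998, that is, if its p-value lies between about 0.046 and 0.05.

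**If twins carry more risk (assumption, 8% in singletons, f = 2%).** At double the risk, the true error is 5.43% at ρ = 0.5 and 5.84% at ρ = 1. At triple the risk and ρ = 1 it is 6.20%.

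**Poisson model-based variance.** The Poisson variance of a log risk is proportional to 1/p; the binomial one is proportional to (1−p)/p. With equal risks in the two arms, the reported-to-true standard error ratio is 1/√[(1−p)·DE].
- 8% risk: 1/√(0.92·1.0392) = 1.023 at f = 2%, ρ = 1; 1/√(0.92·1.0059) = 1.040 at f = 1%, ρ = 0.3.
- 14% risk: 1/√(0.86·1.0392) = 1.058 and 1/√(0.86·1.0059) = 1.075 at the same two corners.

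With a 20% reduction in the active arm, the lowest ratios are 1.018 and 1.048. The standard errors are therefore too large, by about 2-4% at 8% risk and 5-7% at 14% risk, even with twins ignored.

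**Does a robust variance repair it?** In simulations with 16,490 pregnancies per arm (17,000 less 3%) and 200,000 trials per setting, cluster-robust standard errors gave error rates of 0.049 to 0.051 in every setting tried.

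**Power cost.** At f = 2%, ρ = 1 and 8% risk, dividing the evaluable number per arm by 1.0392:
- Africa (34,000·0.375/2·0.97 = 6,184 per arm; 25% reduction): 0.983 to 0.979.
- Asia (34,000·0.5/2·0.97 = 8,245 per arm; 20% reduction): 0.959 to 0.951.
- Overall (20% reduction): stays above 0.999.

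**The case against.** The best defence is that the rule is pre-specified, rarely triggered and nearly harmless. Much of that stands.

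- **Trigger.** At the bottom of the planning range, with 16,490 evaluable pregnancies per arm and a 20% reduction, the primary composite yields about 16,490·(0.08 + 0.064) = 2,375 events for a model with only treatment and site terms. Nothing in the documents suggests that this model would fail.
- **Where failure is plausible.** Rare secondary outcomes are likelier to fail, but SAP 7.5 calls their p-values and intervals descriptive, and SAP 9.5 aims those models at estimation. An inflated type I error matters little there. Neonatal length of stay is handled by time-to-discharge methods, so the rule does not reach every neonatal secondary outcome.
- **Size.** The authors state the 1-2% figure beside the rule. An error of 5.45% needs 2% twins and perfect correlation; at a correlation of 0.5 or less with equal twin risk it is at most 5.23%.
- **Cure and harm.** If the link causes the failure, the refit may also fail, and then there is no interval to be too narrow.

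A reader might infer that the fallback always produces intervals that are too narrow. The documents do not support that. They name no distribution, and a Poisson model-based variance would err the other way. This leaves the rule's error unknown in direction as well as uncorrected. The defence does not explain why clustering must be dropped at all when an independence working correlation has no correlation parameter to estimate.

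**Conclusion.** The point holds as a minor one. On convergence failure the SAP discards a feature that its own text says the design requires, and a better fallback is readily available. The protocol has no such exception, and the SAP does not record the departure.

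Under a binomial model-based variance, standard errors are understated by about 0.3-1.9% and a 5% test runs at about 5.1-5.5%. Under a Poisson one, standard errors are overstated by about 2-7%. These figures rest on the assumed within-pair correlation, twins only, and equal risk in twins; doubling the twin risk raises the upper limit to 5.84%.

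A reader might also infer that the neonatal primary result is unsafe. It is not on this account: failure of that model is unlikely, and even then only a p-value just under the threshold could change sides.

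**What to change.** In SAP 9.3, replace the fallback sentence as follows:
- Name the distribution and link of the main model.
- On convergence failure of a binary neonatal model, fit a log-link Poisson GEE clustered on pregnancy, with independence working correlation and robust (sandwich) standard errors.
- If any imputed data set fails, refit all of them this way before pooling.
- Record the rule in SAP Section 12.

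This keeps the relative risk and corrects the standard error in either direction. The SAP already lists GEE among its abbreviations and cites the method, so nothing foreign is introduced.

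The cost is a few sentences and a negligible loss of power relative to treating infants as independent: for Asia, 0.959 to 0.951 at the extreme. Robust errors remain unreliable for outcomes with very few events, and a log-Poisson model does not resolve sites with no events. Results for such outcomes should be read with that limit in mind.

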7.2 Adjustments for Covariates

As this is a randomized trial and the randomization process was not compromised during execution, the treatment effect estimate from trial is unbiased, even without adjusting for any baseline covariates. Therefore, no adjustments for covariates other than site as a randomization stratification factor are planned for the primary analysis. However, baseline clinical and demographic variables that are known predictors of neonatal and maternal outcomes will be included in secondary analyses of intervention efficacy.

7.3 Missing Data Approaches:

The two primary reasons for missing data are expected to be 1) participant loss to follow-up and 2) lack of record availability of unscheduled clinic visit, hospitalizations and readmissions required to diagnose infections.

Based on the historical data available from the M NH registry, we anticipate that the rate of missing responses due to loss to follow-up for maternal and neonatal morbidity and mortality measures are likely to be 2% or less. This rate has been confirmed based on the pilot data where the current rate is 1.1% for participants loss to follow-up or who were withdrawn or withdrew themselves from study participation.

All suspected infections that cannot be programmatically confirmed will go through a local site and central adjudication process to determine final outcome status using all available information as described in the adjudication plan. We anticipate the rate of cases that cannot be adjudicated to be low; estimates of that proportion will be obtained using pilot data prior to any unmasking or analyses of the main trial data.

For the primary analyses of sepsis and/or death in the ITT population, missing responses due to loss to follow-up and cases of suspected infection that cannot be adjudicated will be included via multiple imputation procedures. Multiple imputation assumes that the mechanism that caused the missing is independent of the value of the unobserved data (i.e. data are missing at random – MAR). Although there is potential that missing data due to record availability may not be MAR, we anticipate this proportion of missing data will be small and multiple imputation processes have been shown to be robust even if the missing mechanism is dependent on the values of the unobserved data, i.e. even if the missing data are non-ignorable non-response. As secondary/sensitivity

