analyses, the primary analyses will also be repeated on the ITT populations using data as available and assuming all missing outcomes are sepsis or death as well as assuming all missing outcomes are not sepsis nor death.

If more than 4% of data in within either or across both arms are missing for any reason, we will conduct additional sensitivity analysis on the effect of missing data on the inference including analyzing data as available and other approaches that will assess the robustness of the findings to different assumptions about the missing data. The exact approaches for these sensitivity analyses will be determined based on the pattern of missingness and detailed in the final study report.

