9.2 Definition of Analysis Variables

As clinical assessments/diagnoses and associated care may lag behind actual occurrence, any infection events, antibiotic use, or other medical care (e.g. admissions, unscheduled visits) documented prior to the end of the relevant visit window will be counted. Mortality outcomes will be defined in accordance with traditional Global Network algorithms only including events occurring specifically within the window detailed in the outcome definition below.

Additionally, most infections are expected to occur within the first week following delivery. Therefore, mothers or infants that are lost to follow-up after completion of a Day 7 visit with no signs or symptoms of infection prior to becoming lost to follow-up will be considered to meet criteria to have the primary outcome ascertained as no infection or death. Mothers or infants lost to follow-up prior to completion of a Day 7 visit with no signs or symptoms of infection will be considered to have missing outcomes.

Variable	Type	Definition
Primary Outcomes		
Maternal death and/or sepsis through 42 days Primary Composite Outcome	Binary	
The event will be defined as “Yes” if either component of this composite outcome is “Yes” and “No” if both components of the composite are “No.” Any subsequent missing values will be included in the primary analyses using multiple imputation procedures.
 
Analysis population(s): ITT (all-comer and high risk; with and without imputation), Per-Protocol

Intrapartum/neonatal death and/or sepsis through 28 days Primary Composite Outcome	Binary	
The event will be defined as “Yes” if either component of this composite outcome is “Yes” and “No” if both components of the composite are “No.” Any subsequent missing values will be included in the primary analyses using multiple imputation procedures.
 
Analysis population(s): ITT (all-comer and high risk; with and without imputation), Per-Protocol

Secondary Outcomes		
Maternal death through 42 days Component	Binary	
The event will be defined as “Yes” if the woman dies prior to 42 days after delivery and “No” otherwise. This outcome measure will be obtained from form MN06 (i.e. presence of a form indicating a death has occurred). If the 42-day outcome is missing and the woman was alive at the last known follow-up, this outcome will be treated as missing when analyzed alone.
 
Analysis population(s): ITT (all-comer and high risk), As Treated

Variable	Type	Definition

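### The imputation model for both primary outcomes leaves out treatment arm, which pulls the relative risk slightly toward 1; the extreme-case analyses also never vary symptom-free losses after Day 7

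*Combined protocol and SAP*

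**What the plan says.** **Imputation.** SAP 9.3 makes multiple imputation part of the primary ITT analysis, "implemented separately for mothers vs. infants via logistic regression imputation using site and high-risk status prior to randomization as covariates". SAP 7.3 says which outcomes are imputed (losses to follow-up, and suspected infections that cannot be adjudicated) but adds no predictors. Of the analysis model, SAP 9.3 says: "The model will include terms for treatment and site". The treatment p-value from that model is the formal test of each primary hypothesis.

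**Expected missingness.** SAP 7.3 expects losses that "are likely to be 2% or less" and reports from the pilot that "the current rate is 1.1% for participants loss to follow-up" or withdrawal.

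**Sensitivity analyses.** SAP 9.3 states that "the primary outcomes will also be analyzed without imputation for individuals in the ITT population". SAP 7.3 and 9.3 add two extreme cases, "assuming all missing outcomes are sepsis or death as well as assuming all missing outcomes are not sepsis nor death". SAP 7.3 calls for further, unspecified analyses only "If more than 4% of data in within either or across both arms are missing for any reason".

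**Day 7 rule.** Under SAP 9.2, "mothers or infants that are lost to follow-up after completion of a Day 7 visit with no signs or symptoms of infection" are scored as having neither infection nor death in the primary composites. The stated reason is that most infections are expected in the first week. Symptom-free losses before Day 7 are missing.

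**The concern.** An imputation model should contain every term of the analysis model, above all the one being tested. Without arm, imputed outcomes in both arms come from a common risk, and any real difference is diluted in proportion to the share imputed. This is the primary estimator for both formal hypotheses, and the omission brings no benefit in return.

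The Day 7 rule raises a separate and smaller question. It is pre-specified and reasoned, and I do not dispute it for the primary analysis. But SAP 9.2 treats the death outcomes, when analysed alone, as missing if a woman was last known alive without a 42-day outcome, or if an infant's 28-day and 42-day outcomes are both missing. Protocol 2.4.7 adds Day 14 and Day 28 contacts to find infection after Day 7. So the documents allow that late events happen, yet none of the named sensitivity analyses re-scores these losses. Because they are not missing for the composites, they do not count toward the 4% trigger for those outcomes either. SAP 8.1 summarises follow-up completion by arm but does not ask for the split around Day 7. A reader could not tell how much of the loss the extreme-case bounds had tested.

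**Working it through.** **Inputs.** 34,000 women allocated 1:1, so 17,000 per arm; maternal control risk 3% and RR 0.80; neonatal control risk from 8% (SAP 6.1); high-risk target RR 0.70 (30% reduction, SAP 6.2); loss 1.1% (pilot), 2% (expected ceiling) and 4% (trigger) (SAP 7.3); final two-sided alpha 0.0499 (SAP 11).

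**The plan's own figure.** The two-proportion formula with pooled variance and no continuity correction, for 3.0% vs 2.4%, two-sided alpha 0.05 and 90% power, gives 15,334 per arm, as in SAP Table 1.

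**Arm omitted.** Let m be the share imputed and r the true RR, with equal missingness in the arms. Imputed outcomes have the pooled risk p0(1+r)/2, so

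RR = [(1−m)r + m(1+r)/2] / [(1−m) + m(1+r)/2].

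For r = 0.80 and m = 2%: (0.98×0.80 + 0.02×0.90)/(0.98 + 0.02×0.90) = 0.802/0.998 = 0.8036. The baseline risk cancels, so the shift is the same for mothers and infants.

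SE(log RR) at 17,000 per arm is 0.0655 for 3.0% vs 2.4% and 0.0392 for 8.0% vs 6.4%. The shift in SE units is ln(RR/0.80)/SE; at 2%, 0.0045/0.0655 = 0.07 and 0.0045/0.0392 = 0.11.

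Power and type I error for the maternal outcome come from 100,000 paired simulated trials: missing completely at random, 20 imputations, Rubin's rules, alpha 0.0499, site and high-risk status ignored.

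| Share imputed | RR for true 0.80 | Shift, maternal SE | Shift, neonatal SE (8%) | Maternal power, arm in / out | Type I error, arm in / out |
|---|---|---|---|---|---|
| 1.1% | 0.802 | 0.04 | 0.06 | 92.3% / 92.0% | 4.95% / 4.7% |
| 2% | 0.804 | 0.07 | 0.11 | 92.3% / 91.7% | 5.1% / 4.6% |
| 4% | 0.807 | 0.14 | 0.23 | 91.8% / 90.5% | 4.9% / 4.0% |

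Neonatal power at 8% risk exceeds 99.9%. For the high-risk cohort, 0.70 becomes 0.703 at 1.1% and 0.705 at 2%. At r = 1 the formula returns exactly 1. A harmful effect is diluted in the same way: 1.20 becomes 1.193 at 3%.

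**Day 7 rule.** Let L be total loss per arm and f the fraction of it lost symptom-free after Day 7. The documents do not give f, so I take 0, 0.5 and 1. With all missing outcomes set to events,

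RR = [(1−L)p0·r + L(1−f)] / [(1−L)p0 + L(1−f)], with p0 = 0.03 and r = 0.80.

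| Loss per arm | f = 0 | f = 0.5 | f = 1 |
|---|---|---|---|
| 1.1% (187 women) | 0.854 | 0.831 | 0.800 |
| 2% (340 women) | 0.881 | 0.851 | 0.800 |

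At f = 1 the supposed worst case leaves the estimate untouched.

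**Tipping point at f = 1.** Observed events are 17,000×0.989×0.024 = 403.5 vs 17,000×0.989×0.03 = 504.4 at 1.1% loss, and 399.8 vs 499.8 at 2%. I add events to azithromycin losses only until |z| for log RR falls below 1.961. That takes 42 of 187 (22%) at 1.1% loss, or 41 of 340 (12%) at 2%.

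**The case against.** **The SAP may not mean to leave arm out.** SAP 7.2 plans no covariates other than site for the primary analysis, yet that model contains treatment, so the SAP's word for covariates may not include arm. This is possible. But an analyst who codes the stated predictor list will omit arm, and nothing in SAP 7.3 or 9.3 says that imputation is done by arm. If arm was intended, the fix is only a clarification.

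**The effect is immaterial, and the ITT analysis without imputation already shows it.** The first half is right at the documented loss rates, and the Day 7 rule makes the imputed share of losses smaller still. Comparing the two planned analyses would indeed expose the dilution. But a sensitivity analysis does not correct the headline estimate.

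**The simulation covers only part of what is imputed.** This stands. Suspected infections that cannot be adjudicated probably carry a much higher risk than average, and the figures above assume missingness completely at random. SAP 7.3 expects such cases to be few.

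**The Day 7 re-run is a matter of preference.** Much of this stands. The upper bound gives a 100% event rate to people seen well at Day 7. More realistically, suppose azithromycin losses had the full 3% risk after Day 7 and placebo losses none. The RR would be (403.5 + 0.03×187)/504.4 = 0.811 at 1.1% loss, or (399.8 + 0.03×340)/499.8 = 0.820 at 2%. SAP 8.1 also reviews withdrawal reasons by arm, and SAP 9.3 plans time-to-event curves. Neither of these varies the scoring of the late losses.

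**Conclusion.** Both parts hold, as a minor matter to consider. As written, the imputation model omits arm and attenuates the RR by 0.002 to 0.004 at 1.1% to 2% imputed, and by 0.007 at 4%. The test becomes slightly conservative. Type I error is not inflated, the ITT analysis without imputation is unaffected, and no conclusion is expected to change. These figures assume equal, completely random missingness and the planning risks.

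The Day 7 point is a gap in the sensitivity analyses and not a demonstrated bias. Its size depends on the share of loss that falls after Day 7, which is not reported. The tipping points (12% to 22% late events among azithromycin losses and none among placebo losses) suggest that the check will reassure.

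**What to change.** 1. In SAP 9.3, add treatment arm to the imputation model, or impute within arm. In simulation this returns an RR of 0.80 at every missing share from 1.1% to 4%. The cost is one covariate in the code.
2. Keep the Day 7 rule for the primary analysis. Add one sensitivity analysis that repeats the two extreme cases with symptom-free post-Day-7 losses classed as missing. The cost is one re-run with a different missing-data flag. The bounds will be wider, and the upper one must be read as a bound and not as an estimate.
3. Report the number of such losses by arm alongside the disposition summary in SAP 8.1.
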